AUC	Area Under the (time-concentration) Curve
BCMA	B-Cell Maturation Antigen
BSC	Biological Safety Cabinet
CA	Cytogenetic Abnormality
CAR	Chimeric Antigen Receptor
CBC	Complete blood count
CDR	Complementarity-Determining Regions
CLL	Chronic Lymphocytic Leukemia
CMC	Chemistry, Manufacturing, and Controls
CNS	Central Nervous System
CR	Complete Response
CrCl	Creatinine Clearance
CRS	Cytokine Release Syndrome
CSF	Cerebrospinal fluid
CT	Computed Tomography
CTCAE	Common Terminology Criteria for Adverse Events
DMF	Drug Master File
DNA	Deoxyribonucleic acid
ECG	Electrocardiogram
FHCRC	Fred Hutchinson Cancer Research Center
iFISH	Interphase Fluorescence In-Situ Hybridization
FLC	Free light chain
GLP	Good Laboratory Practice
GM-CSF	Granulocyte-Macrophage colony-stimulating factor
GMP	Good Manufacturing Practice
GVHD	Graft-versus-host disease
HAMA	Human anti-mouse antibody
HAS	Human Serum Albumin
HBV	Hepatitis B virus
HCV	Hepatitis C virus
HIV	Human immunodeficiency virus
HPLC	High Performance Liquid Chromatography
HR	Hazard Ratio
IFN- γ	Interferon-gamma
IL	Interleukin
IMID	Immunomodulatory drug

IMWG	International Myeloma Working Group
IND	Investigational New Drug(application)
IV	Intravenous(ly)
MFC	Multi-parameter flow cytometry
MHC	Major histocompatibility complex
MM	Multiple Myeloma
MOI	Multiplicity of infection
MRD	Minimal Residual Disease
MTD	Maximal Tolerated Dose
NCI	National Cancer Institute
NDMM	Newly Diagnosed Multiple Myeloma
NGS	Next Generation Sequencing
NOAEL	No Observed Adverse Effect Level
NSAID	Non-steroidal anti-inflammatory drug
MRD	Minimal Residual Disease
MRSD	Maximum Recommended Starting Dose
MSSD	Maximum Safe Starting Dose
NDA	New Drug Application
ODD	Orphan Drug Designation (application)
OS	Overall Survival
PFS	Progression-Free Survival
PI	Proteasome inhibitor
PK	Pharmacokinetic
PR	Partial Response
PRBC	Packed Red Blood Cells
PRES	Posterior Reversible Encephalopathy Syndrome
SAE	Serious Adverse Event
sCR	Stringent Complete Response
SEM	Standard Error of the Mean
SIFE	Serum immunofixation electrophoresis
SM	Starting Materials
SPEP	Serum protein electrophoresis
SPD	Sum of the Products of the Maximal Perpendicular Diameters
TK	Toxicokinetic(s)
TLS	Tumor Lysis Syndrome
TNF α	Tumor-necrosis factor alpha
UIFE	Urine immunofixation electrophoresis
UPEP	Urine protein electrophoresis
VGPR	Very Good Partial Response

1 Introduction

1.1 Study Objectives

1.1.1 Primary Objective

To assess Minimal Residual Disease (MRD)-negative Complete Response (sCR) rate after consolidation treatment with Descartes-11 in patients with high-risk myeloma who have residual disease following induction therapy.

1.1.2 Secondary Objectives

A bar chart illustrating the distribution of a variable across 10 categories. The x-axis represents the categories, and the y-axis represents the frequency or value of the variable. The distribution is highly right-skewed, with the highest frequency in the first category and a long tail extending to the tenth category.

Category	Value
1	100
2	85
3	75
4	65
5	55
6	45
7	35
8	25
9	15
10	10

1.1.3 Exploratory Objectives

For more information, contact the Office of the Vice President for Research and Economic Development at [contact] or [contact].

1.2 Background and Rationale

1.2.1 Epidemiology of High-Risk Multiple Myeloma

In 2018, there were over 30,000 new cases of multiple myeloma (MM) and over 10,000 deaths from this disease.¹ MM is the second most common hematological malignancy in adults after lymphoma, with a median survival diagnosis of about 10 years.² A subgroup of myeloma patients carry features that confer poor risk and median survival is usually less than 4 years³. Historically, these poor-prognosis patients have been identified using clinical biomarkers such as β 2-microglobulin and albumin. Based on these two markers, patients were classified into 3 risk-category groups in the International Staging System for Myeloma (ISS). With the advent of analytical methods that can diagnose chromosomal translocations, such as Fluorescence In Situ Hybridization (FISH), genomic changes were found to be independent risk factors for prognosis of multiple myeloma regardless of treatment. Based on the International Myeloma Working Group (IMWG) consensus, high-risk chromosomal instabilities include translocations of the IgH locus on chromosome 14 with an oncogene such as FGFR3/MMSET on chromosome 4 (t(4;14)) or c-MAF on chromosome 16 (t(14;16)) or MAFB on chromosome 20 (t(14;20)).³ These translocations are observed in 15%, 4% and 1% of the newly diagnosed multiple myeloma (NDMM) patients, respectively.^{4,5} Beside translocations, deletion of p53 on chromosome 17p, non-hyperdiploid karyotype, deletion 13 by karyotype, and gain 1q/loss of 1p (seen in 7%, 50% 44%, 30% of newly diagnosed multiple myeloma patients, respectively) are also associated with poor survival.^{4,5} Each of these genomic aberrations has independently similar impact on the outcome of multiple myeloma patients while their combination further reduces overall survival. For example, the triple combination of an adverse IgH translocation, gain(1q), and del(17p) was associated with a median overall survival (OS) of 9.1 months.⁶ Chromosomal aberrations showing improved outcomes were also identified, such as trisomies 3 and 5.^{7,8} When both favorable and unfavorable cytogenetics coincide in the same patient, the unfavorable findings tend to dominate the clinical picture^{8,9}.

1.2.2 Definition of High-Risk Multiple Myeloma

High risk disease is defined by IMWG consensus.³ IMWG defines high-risk disease as either R-ISS Stage III or by one or more high-risk cytogenetic abnormalities (CAs).³ R-ISS Stage III is defined as serum β -microglobulin ≥ 5.5 mg/L and either high risk CA by iFISH or high LDH.¹⁰ High-risk CAs are 1) t(4;14), t(14;16), t(14;20), del(17/17p), non-hyperdiploid karyotype, gain(1q), del 13, gain 1q, or a high-risk signature on gene expression profile (GEP).

1.2.3 Treatment of High-Risk Multiple Myeloma

Bortezomib partly overcomes the adverse effect of t(4;14) and possibly del(17p) on CR, PFS, and OS.¹¹⁻¹⁵ A meta-analysis of 4 randomized trials showed that the odds of post-transplantation deep response rate (VGPR or better) were similar in high-risk cytogenetics (del(17p) and t(4;14)) and standard risk cytogenetics when bortezomib was used in the induction treatment.¹³ An integrated analysis of phase III trials demonstrates PFS benefit in patients with t(4;14) but lacking del(17p) and in del(17p) lacking t(4;14) but not in patients carrying both abnormalities.¹⁶ Thus, a bortezomib-based induction regimen, and if patient is eligible followed by high dose therapy/ASCT, ideally shortly after completion of 6-8 cycles of initial therapy, is the recommended treatment in NDMM with high-risk features.³ Typically after 3-4 cycles of multi-drug induction regimen, treatment is paused briefly for stem cell collection and then treatment is completed to 6-

8 cycles. However, this regimen results in MRD-negativity in only 20% of patients¹⁷ and CR only in 30-35%^{18,19} of patients, and the median Event-Free Survival remains at 14-24 months depending on the cytogenetic abnormality.¹¹ In patients who do not receive ASCT in frontline therapy but receive PI/lenalidomide based regimen, achieve 15% CR²⁰ and with addition of cyclophosphamide 35% CR with only half of them being MRD negative.²¹ Thus, there is clear need for intensifying the upfront treatment in this patient population. Despite this need, there is no consensus on the appropriate subsequent therapy for these patients. Prevailing approaches include proteasome inhibitor/immunomodulatory drug combination maintenance, a second autotransplant, or even an allogeneic transplant.^{3,16,22} A meta-analysis of 4 European trials showed that double ASCT combined with a bortezomib-based treatment regimen partially abrogates poor PFS in patients carrying both t(4;14) and del(17p)¹⁶, and limited data with RVD maintenance given up to 3 years post-transplant suggests some benefit in a group with del p53, del 1p; (t(4;14) or t(14;16)) with an sCR rate of 50%.²³ Although long-term PFS can be achieved with allogeneic HSCT, the benefits of graft-versus-myeloma effect are limited by high treatment-related mortality (TRM), approaching 40% for myeloablative transplantations.²⁴ Clinical trial enrollment for high-risk NDMM is therefore recommended by multiple expert groups.^{18,22}

1.2.4 MRD as Clinical Outcome in Myeloma Patients

MRD testing in NDMM patients following first-line therapy was originally developed using multi-color flow cytometry,²⁵ which has been widely used in several trials for multiple myeloma.^{26,27} Due to their superior sensitivity, genomic testing like Next Generation Sequencing (NGS) or IgH became the preferred method of MRD testing. Specifically, flow cytometry-based MRD assays can detect 1 myeloma cell in 100,000 bone marrow cells; current genetic MRD assays can detect 1 myeloma cell in 1,000,000 bone marrow cells.²⁸ This is important because the depth of MRD correlates with PFS.^{29,30,31,32} Data are limited in patients with high-risk myeloma but also show that MRD is an independent risk factor in high-risk myeloma.³³ Therefore multiple expert reviews propose that MRD testing should and will become a primary regulatory efficacy endpoint.^{3,22,34}

1.2.5 CAR-T Therapy in Multiple Myeloma

B-cell maturation antigen (BCMA), also known as tumor necrosis factor receptor superfamily member 17 (TNFRSF17) or CD269, is consistently and selectively expressed on normal plasma and myeloma cells.³⁵ For this reason, it is a preferred target antigen for CAR immunotherapy of MM. Upon engagement by its ligands, i.e., TNFSF13 (APRIL: a proliferation-inducing ligand; CD256) and TNFSF13B (BAFF: B cell-activating factor; also known as BLYS or CD257), BCMA supports survival of plasma cells.³⁶

A CAR construct against BCMA was originally developed at the National Cancer Institute (NCI) and was introduced into CD3+ cells using a viral transduction system that inserts the gene permanently into the genome of the T-cell. At the maximum tolerated dose (MTD) of 9x10⁶ cells/kg, 63% of the patients achieved very good partial response (VGPR) or better.³⁷ Given the promising efficacy of the virally transduced anti-BCMA CAR T-cells, several other groups created permanently modified anti-BCMA CAR T-cells now in clinical testing. Bluebird Bio's anti-BCMA-CAR T-cell construct has completed its phase II trial in relapsed refractory patients who progressed after at least 2 lines of therapy demonstrated an impressive 85% overall response rate (ORR) with 45% of the patients having CR or better response.^{38,39} Another product originally developed in China was recently evaluated in relapsed refractory patients during a Phase I multi-

center trial in USA and showed 100% ORR with 61% of the patients achieving CR or better.⁴⁰ Similar highly promising result are reported for several other anti-BCMA CAR-T cell products developed by different groups confirming the high potency of anti-BCMA CAR T-cells in killing myeloma cells. More importantly, this potency is seen across all risk groups, including patients with adverse cytogenetics suggesting that CAR T-cell mediated killing is independent of resistance mechanisms generated by high-risk chromosomal aberrations.

The potency of virally transduced CAR therapies comes with significant risks. All clinical trials of virally transduced CAR T-cells have recorded serious instances of cytokine release syndrome (CRS) and neurological toxicity. In the recent American Society of Blood and Marrow Transplant (ASBMT) consensus meeting, CRS was defined as “a supraphysiologic response following any immune therapy that results in the activation or engagement of endogenous or infused T cells and/or other immune effector cells. Symptoms can be progressive, must include fever at the onset, and may include hypotension, capillary leak (hypoxia) and end organ dysfunction.”⁴¹ CRS is a prototypical systemic inflammatory response syndrome that occurs hours to days after CAR T-cell infusion. Signs and symptoms include fever, myalgia, malaise, and, in more severe cases, a capillary leak syndrome associated with hypoxia, hypotension, and occasionally renal dysfunction and coagulopathy. Peak CAR T-cells as a result of *in vivo* proliferation has been strongly associated with the severity of CRS in many CAR T-cell studies.^{42,43} The proliferation of CAR T-cells upon engagement with target antigen drives them to secrete cytokines that initiates a cascade of systemic inflammatory events. Among all cytokines elevated during CRS, IL-6 plays a central role as neutralization of this cytokine quickly and effectively reverses clinical deterioration in most cases.

The first presenting symptom of CRS is usually fever associated with mild constitutional symptoms.^{42,44-46} In a number of patients, the initial mild symptoms progress over the course of hours to days and turn into a systemic inflammatory syndrome characterized by sinus tachycardia, hypotension and hypoxia. In severe cases, patients may require mechanical ventilation and vasopressors. CRS can start as early as the day of CAR T-cell infusion and in most cases it occurs within the first 14 days following the infusion. Severe cases appear to occur closer to the time of infusion and the severity of CRS was reported to correlate with peak CAR T-cell levels as mentioned above as well as disease burden^{42,43} and addition of preconditioning chemotherapy.^{43,44,46,47}

Neurotoxicity associated with CAR T-cell treatment, now named “Immune effector cell-associated neurotoxicity syndrome” (ICANS) in the ASBMT consensus panel document, is described as “a disorder characterized by a pathologic process involving the central nervous system following any immune therapy that results in the activation or engagement of endogenous or infused T cells and/or other immune effector cells. Reported neurologic toxicities include headaches, confusion, alterations in wakefulness, hallucinations, dysphasia, ataxia, apraxia, facial nerve palsy, tremor, dysmetria, and seizures^{43-45,48-53}. Neurotoxicity has been reported in several anti-CD19 CAR T-cell trials and severe cerebral edema lead to death in a small number of patients^{54,55}. However, it has occurred less frequently in anti-BCMA CAR T-cell trials^{37,39}. Factors that underlie CRS like peak CAR T-cell levels^{44,46,54,56} or cytokine levels^{43,48,52,57} are also associated with neurotoxicity.

Several grading systems have been developed for CAR T-cell-related CRS and neurotoxicity and this protocol uses grading developed based on ASBMT consensus criteria.⁴¹

1.2.6 Rationale for Current Protocol

Currently, the mainstay of treatment for high-risk NDMM is timely induction with a proteasome inhibitor/immunomodulatory drug combination followed by ASCT, which should be completed within 12 months of diagnosis. The ideal consolidation therapy in this setting would be effective in targeting myeloma clones that are resistant to the proteasome inhibitor/immunomodulatory drug combination and chemotherapy without any risk of toxicity that would delay ASCT or that would not be tolerated by a transplant-ineligible patient. A non-toxic anti-BCMA CAR T-cell therapy would provide one such therapy.

Severe CRS and neurotoxicity have only been observed in the context of CAR T-cells that are permanently modified by gene transfer. Under conditions of *genomic* modification, once CAR T-cells are engrafted, they proliferate exponentially and generate very high numbers of cells without the need for a repeat infusion. While this may provide control of the disease, rapid and uncontrolled CAR T-cell proliferation also can cause severe toxicity. In contrast, in CAR T-cells transfected with mRNA, the CAR T-cell's mRNA and CAR protein is halved with each T-cell division, effectively limiting the proliferative capacity and total circulating numbers of CAR+ T-cells. This key modification dramatically limits the potential for CRS and neurotoxicity. Furthermore, because mRNA has an inherent rate of degradation, CAR expression gradually declines to zero even in the absence of target antigen. These pharmacological properties resemble conventional drugs with predictable pharmacokinetics (PK) and pharmacodynamics (PD), properties that would be difficult or impossible to obtain with genetically modified CAR T-cells. More predictable PK in mRNA-transfected CAR T-cell activity affords the opportunity for systematic repeat dosing to maintain or, as needed, intensify anti-tumor activity. In preclinical studies, repeat dosing of mRNA-transfected CAR T-cells has shown efficacy in ALL⁵⁸, AML, breast cancer⁵⁹, neuroblastoma⁶⁰, mesothelin-expressing cancers⁶¹ and EGFR-expressing cancers.⁶²

1.2.7 Rationale for use of MRD testing as Primary Endpoint

As stated above, MRD is strongly correlated with the gold standard of PFS, which can take over 2 years to reach even in a high-risk myeloma patient population with the use of novel agents. Demonstrating MRD negativity in the context of safety and other endpoints therefore will be highly informative in assessing Descartes-11 for treatment of high-risk NDMM patients. In the era of novel agents, sCR rate in high-risk NDMM patients is reported to be 10% after induction treatment, 20% after ASCT and 50% after 3 years of RVD.²³ Similarly, CR was seen in less than 10% of high-risk patients post-induction, 20% of patients after ASCT and 50% after 2 years of bortezomib maintenance in the HOVON trial.¹⁹ Finally, the large PETHEMA trial using bortezomib/immunomodulatory drug combination reported 35% CR rate in high-risk patients following transplant. In a smaller series in which 25% of the patients were high risk, investigators tested proteasome inhibitor-based combination as an induction therapy followed by ASCT and reported MRD-negative CR in 20% of the patients after transplant.¹⁷ To our knowledge there is only one reported study that investigates the impact of each phase of treatment onto the depth of response which used flow cytometry for MRD assessment and showed that following induction therapy 1%, after first transplant 0.24% and after second transplant 0.1% of the cells were abnormal.⁶³ The greatest MRD negativity reported for high-risk patients in a small series (5 patients) in which 44% of the patients achieved MRD negativity after 8 cycles of carfilzomib, lenalidomide and dexamethasone combination which did not deepen after ASCT or 1 year of lenalidomide maintenance.⁶⁴ Thus, achieving more than 20% MRD negativity pre-ASCT in patients receiving bortezomib based regimen or 50% in all newly diagnosed patients after completing frontline therapy will be a significant improvement in NDMM with high-risk features. In this protocol, bone marrow will be evaluated by IgH/IgK gene rearrangements to search for MRD up to 1 in 10^5 cells.

1.3 Study Drug

1.3.1 Description

Descartes-11 is an autologous CD8+ T-cell product modified to express a humanized anti-BCMA CAR.

1.3.2 Route of Administration and Dosing Regimen

[REDACTED]

1.3.3 Nonclinical and Clinical Data

Please refer to Investigator Brochure for a detailed description of nonclinical and clinical data.

2 Eligibility and Enrollment

2.1 Eligibility Criteria

2.1.1 Inclusion Criteria

The following inclusion criteria will be applied at Screening, unless another evaluation time point is specified:

1. High-risk multiple myeloma patients (defined below) who complete pre-transplant induction treatment anti-myeloma drug combination (minimum 2 drugs).
2. Following completion of the pre-transplant induction regimen, patients must have residual disease measured by at least one of the following markers:
 - a. Serum M-protein detectable by immunofixation
 - b. Urine M-protein detectable by immunofixation
 - c. Abnormal FLC ratio
 - d. A biopsy-proven plasmacytoma or residual disease on imaging of a spot that was known to have plasmacytoma
 - e. Evidence of clonal cells in immunohistochemistry defined as Kappa/Lambda <4:1 or >1:2 after counting ≥ 100 plasma cells
 - f. Evidence of MRD detected by DNA-based or flow cytometry approaches
3. Patients must have high-risk multiple myeloma based on IMWG consensus as defined by R-ISS Stage III¹⁰ or high-risk CA³.
 - a. R-ISS Stage III is defined as having serum β -microglobulin ≥ 5.5 mg/L and either a high risk CA by iFISH or high LDH.
 - b. High-risk CAs are defined as having 1) t(4;14), t(14;16), t(14;20), or del(17/17p) in at least 20% of the cells; 2) any non-hyperdiploid karyotype, 3) gain(1q); 4) del 13; 5) gain 1q; or 6) a high-risk signature on gene expression profile (GEP).
4. There should be at least 7 days between the last dose of anti-myeloma drug and first Descartes-11 infusion.
5. Toxicities from prior therapies must have resolved to Grade 2 or less according to the CTCAE 5.0 criteria, or to the subject's pre-therapy baseline at the time of first cell infusion.
6. Patients must have signed written, informed consent.
7. Patients must be 18 years of age or older at the time of enrollment.
8. Patients must have clinical performance status of ECOG 0-2.
9. Patients must be seronegative for HIV.
10. Patients must be seronegative for hepatitis B (HBV) antigen; or, if the patient is positive for the hepatitis B antigen test, he or she must be negative for HBV DNA and must agree to use Hepatitis B prophylaxis as per institution guideline and/or principal investigator discretion.

11. Patients must be seronegative for hepatitis C (HCV) antibody; or, if the hepatitis C antibody test is positive, the patient must be tested for the presence of viremia by RT-PCR and must be HCV RNA negative.
12. Patients must have adequate vital organ function as defined by the following criteria:
 - Bone marrow function defined by absolute neutrophil count (ANC) >1000 cells/mm³ and platelet count $>50,000$ cells/mm³
 - Serum ALT and AST less or equal to 3 times the upper limit of the institutional normal;
 - Total bilirubin ≤ 2.0 mg/dL, except in patients with Gilbert's Syndrome, who must have a total bilirubin less than 3.0 mg/dL;
 - Normal cardiac ejection fraction ($\geq 45\%$ by echocardiography) and no evidence of hemodynamically significant pericardial effusion as determined by an echocardiogram within 6 months of the start of the leukapheresis; AND
 - Creatinine Clearance (CrCl) ≥ 30 mL/min or 30 mL/min/1.73 m².

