3.2.1 Overall Treatment Design

The overall schedule of treatment for this Phase II study is illustrated in [Figure 1](#). Steps shown prior to Screening affect eligibility but are not part of the study.

Eligible patients will receive an induction regimen with at least 2 anti-myeloma agents excluding monoclonal antibodies. After completion of the full pre-transplant induction regimen prior to high-dose chemotherapy and ASCT, eligible patients must have measurable residual disease as defined in the Eligibility Criteria. A patient can be screened and enrolled at that point.

Descartes-11 treatment will begin at least 7 days after the patient's final dose of anti-myeloma therapy. The dose of cells will be 25×10^6 cells/kg, and doses will be given on Days 1, 4, 8, 11, 15, 18 (i.e., total dose of 150×10^6 cells/kg). Weight obtained during Screening Visit will be used for dose calculation. Doses are expressed as the number of live CAR+ cells.

After completing all cell infusions, the patient will be evaluated for clinical response and then followed-up for up to 36 months unless they meet off-study criteria outlined in [Section 4.5.2](#). During the follow-up period, if indicated, any additional induction therapy, high-dose chemotherapy and/or ASCT may be administered at the discretion of the investigator. Except for experimental agents that are not approved for myeloma treatment, treatment will be left to the investigator's discretion. The patient will be followed every 3 months for the first year, every 6 months for the second year and one time during the third year.

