4.4 Treatment Response Assessment

IMWG response criteria published in 2016 will be used for response assessment. Below is a table summarizing the parameter to stratify a response.

Table 1. IMWG Response Criteria⁶⁸

Response Category	Parameters
Stringent complete response	Complete response as defined below plus normal FLC ratio and absence of clonal cells in bone marrow biopsy by immunohistochemistry (Kappa/Lambda \leq 4:1 or \geq 1:2) or kappa and lambda patients, respectively, after counting \geq 100 plasma cells
Complete response	Negative immunofixation on the serum and urine and disappearance of any soft tissue plasmacytomas and $<5\%$ plasma cells in bone marrow aspirates
Very good partial response	Serum and M-protein detectable by immunofixation but not on electrophoresis or $\geq 90\%$ reduction in M-protein plus urine M-protein level <100 mg/24 hours
Partial response	$\geq 50\%$ reduction of serum M-protein plus reduction in 24 hours urinary M-protein by $\geq 90\%$ or to <200 mg/24 hours. If the serum and urine M-protein are unmeasurable, a $\geq 50\%$ decrease in the difference between involved and uninvolved FLC levels is required in place of the M-protein criteria. If the serum and urine M-protein as well as serum-free light chains are unmeasurable, $\geq 50\%$ reduction in plasma cells is required, provided baseline bone marrow plasma-cell percentage was $\geq 30\%$. In addition to these criteria, if present at baseline, $\geq 50\%$ reduction in size (sum of the products of the maximum perpendicular diameters (SPD) of measured lesions) of soft tissue plasmacytomas is also required.
Minimal response	$\geq 25\%$ but $\leq 49\%$ reduction of serum M-protein and reduction in urine M-protein by 50-89%. In addition to these criteria, if present at baseline, $\geq 50\%$ reduction in size (sum of the products of the maximum perpendicular diameters of measured lesions) of soft tissue plasmacytomas is also required.

Response Category	Parameters

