5.5 Stopping Rules and Study Termination

Premature termination of the clinical trial may occur because of a regulatory authority decision, change in opinion of the IRB or medical monitor. Additionally, recruitment may be stopped for reasons of particularly low recruitment, protocol violations, or inadequate data recording. Specifically, study will be stopped if:

- Study Sponsor or a Regulatory Body decides for any reason that subject safety may be compromised by continuing the study.
- The Sponsor decides to discontinue the development of the intervention to be used in this study.

The study will be **paused if:**

- There is death that is reasonably attributed to study drug within the first 30 days after first infusion
- Two subjects with Grade 4 adverse events to vital organs that are assessed as probably or definitely related to study drug within the 14 days after last infusion

If the study is paused for the reasons above, the PI and members of the study team will meet in person or by teleconference within 24 hours of the event to have a thorough discussion of the event. Meeting minutes capturing the review of any ongoing investigations, including next steps in the management of the subject and any proposed changes to the protocol will be forwarded to the medical monitor. If all parties agree as to the event resolution, then the pause will be lifted. If the study is paused for manufacturing reasons, the Sponsor will make recommendations for process improvements to be implemented. Pending successful completion of a process validation run, the manufacturing pause will be lifted.

6 Statistical Considerations

Statistical analysis will be described in a separate Statistical Analysis Plan.

Briefly, with respect to sample size: the primary endpoint will be the proportion of responders, i.e., patients who are MRD-negative with sCR at the Day 28 Visit. This is an open-label study, and the null hypothesis is that the responder rate will not differ from the natural rate of MRD-negative sCR at the end of consolidation, as observed in the literature. We determined that this natural rate is 10%.^{19,31,64,69-73} For purposes of power calculations, we assume that the response rate will be 35%. With these assumptions, a sample size of 34 will provide 80% power to detect a one-tailed difference at the 95% confidence level.

7 Ethical Considerations

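### Inclusion item 2e prints as evidence of clonal cells the kappa/lambda range that Table 1 treats as their absence, so a patient without residual disease can meet inclusion criterion 2

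*Combined protocol and SAP*

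**What the plan says.** Section 2.1.1, criterion 2, requires that after induction "patients must have residual disease measured by at least one of the following markers", and lists six, a to f. Item 2e is the marrow immunohistochemistry marker: "Evidence of clonal cells in immunohistochemistry defined as Kappa/Lambda <4:1 or >1:2 after counting" at least 100 plasma cells. It does not assign either bound to a light-chain type. Item 2f is the MRD marker: "Evidence of MRD detected by DNA-based or flow cytometry approaches".

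Table 1 in Section 4.4 defines stringent complete response as complete response plus a normal FLC ratio and "absence of clonal cells in bone marrow biopsy by immunohistochemistry". The range given for that absence is kappa/lambda at most 4:1 or at least 1:2, followed by "or kappa and lambda patients, respectively, after counting" at least 100 plasma cells. The first word of that phrase is evidently meant as 'for', which assigns 4:1 to kappa patients and 1:2 to lambda patients.

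Section 3.2.1 gives no ratio of its own: "eligible patients must have measurable residual disease as defined in the Eligibility Criteria". The primary objective (Section 1.1.1) concerns patients "who have residual disease following induction therapy". The primary endpoint (Section 6) is "the proportion of responders, i.e., patients who are MRD-negative with sCR at the Day 28 Visit".

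**The concern.** Item 2e and Table 1 use the same two bounds in the same direction but attach opposite labels. Item 2e appears to be Table 1's range for a non-clonal marrow with the equality signs dropped and the direction left unreversed. Because one marker is enough, 2e alone can satisfy criterion 2, and nothing elsewhere in the eligibility text corrects its inequality signs.

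Two things are at stake. The first is the population: a patient negative on every other marker and with a non-clonal marrow meets the printed criterion, although the primary objective excludes that patient. The second is the endpoint, which is a status at Day 28 in a single-arm trial and not a change from baseline. A patient already in MRD-negative sCR at entry who stays there counts as a responder without any treatment effect. A patient in sCR who is MRD-positive is a different case. That patient is properly eligible under 2f and is no part of this concern.

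**Working it through.** **Inputs.** The ratio bounds come from Section 2.1.1 item 2e and from Table 1. The one-marker rule comes from criterion 2. The sample size of 34 and the null rate of 10% come from Section 6.

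**One example.** Take kappa/lambda = 1.5:1.
- Table 1: 1.5 is at most 4 and at least 0.5, so clonal cells are absent in kappa and lambda patients alike.
- Item 2e: 1.5 is below 4 and above 0.5, so there is evidence of clonal cells, whether 2e is read as printed or by light chain.

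**All splits of 100 cells.** Let k be the number of kappa cells, k = 0 to 100, with ratio k/(100 − k). The ratio is exactly 4:1 at k = 80. It cannot be exactly 1:2 with 100 cells; it first exceeds 1:2 at k = 34.

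*Literal reading (below 4:1 or above 1:2, no light-chain split).* Every ratio satisfies at least one of the two conditions, so 101 of 101 splits meet 2e and the item excludes nobody.

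*Reading by light chain, as in Table 1.*

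| | Kappa patients | Lambda patients |
|---|---|---|
| Table 1 non-clonal | k = 0–80: 81 splits | k = 34–100: 67 splits |
| of these, meet 2e | 80 (all but k = 80) | 67 |
| Remaining (clonal) | k = 81–100: 20 splits | k = 0–33: 34 splits |
| of these, meet 2e | 0 | 0 |

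Under this reading the rule is inverted: 80 + 67 = 147 of 81 + 67 = 148 non-clonal splits qualify, and 0 of 20 + 34 = 54 clonal splits do. The counts describe the wording only. Splits are not equally likely in patients, so the counts are not patient proportions.

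**Effect on the result.** One patient already in MRD-negative sCR who remains so adds 1/34 = 2.9 percentage points to the observed rate.

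The effect on the test needs a success cut-off, which Section 6 does not give. Assume an exact one-sided binomial test at 5%. Seven or more responders of 34 is then the smallest qualifying cut-off: P(X ≥ 7 | 34, 0.10) = 0.048, whereas six or more gives 0.119. With one certain responder, success needs at least 6 of the other 33, who respond at rate p:

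| p for the other 33 | Mean overall rate (1 + 33p)/34 | P(X ≥ 6 given 33, p) |
|---|---|---|
| 0.02 | 4.9% | 0.00004 |
| 0.05 | 7.8% | 0.0054 |
| 2.4/33 = 0.073 | 10.0% | 0.030 |
| 0.10 | 12.6% | 0.106 |

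The comparison is 0.048 with no such patient and everyone at 10%. Whether the false-positive rate rises therefore depends on whether the 10% literature rate already includes patients in response at entry. If it does, the third row applies and there is no inflation. If the other 33 respond at 10% on their own, the rate rises to 10.6%.

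**The case against.** The strongest objection is that this is a reversed-sign slip whose intent is obvious. Criterion 2 speaks of residual disease, 2e is headed as evidence of clonal cells, and Table 1 prints the range for absence, so a pathologist would probably apply the intended rule. To enter wrongly, a patient must also be negative on immunofixation, FLC ratio, plasmacytoma and MRD, and marrow flow cytometry is a scheduled screening test, so 2f will normally be assessed by at least that method. No harm to the result has been shown. The false-positive range rests on an assumed cut-off and runs from no inflation to inflation.

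Much of this stands. The route is narrow, sites may well follow the intent, and the false-positive figures are illustrations and not estimates. The split counts add little beyond the single example. Table 1 is also garbled where it assigns the bounds to light-chain types, and a sign lost in converting the PDF cannot be wholly excluded. However, two signs would have to have been reversed, and the neighbouring inequality signs read sensibly.

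The conflict itself survives. Eligibility is confirmed from source documents against the printed criterion. A site applying the intended rule departs from the text, while a site applying the text can enrol a patient without residual disease. The 1.5:1 example does not depend on how the garbled phrase is read.

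**Conclusion.** The concern holds. As printed, 2e either admits every ratio (literal reading) or admits the non-clonal range and rejects the clonal one (light-chain reading, differing from Table 1 only at exactly 4:1 in kappa patients or 1:2 in lambda patients). Under both readings a non-clonal marrow can satisfy criterion 2. Under the second, clonal marrows fail 2e, although those patients may still qualify through another marker.

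That the wording is wrong is established with high confidence. Its effect on the trial is not: the number of patients entering through 2e alone is unknown and may be zero. Any who were already MRD-negative sCR and stayed so would each add 2.9 percentage points, assuming 34 evaluable patients. The effect on the test cannot be fixed from the documents. This should be corrected because it is an operative threshold defining the study population, but it does not by itself invalidate the design.

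**What to change.** Reconcile 2e with Table 1 by making it the exact complement of the protocol's own definition of absence: kappa/lambda above 4:1 in kappa patients, or below 1:2 in lambda patients, after counting at least 100 plasma cells. With that wording all 54 clonal splits and none of the 148 non-clonal splits meet 2e, so the two definitions neither overlap nor leave a gap. In the same amendment, correct the word in Table 1 that introduces the light-chain types.

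Optionally, report beside the Day 28 rate how many treated patients met criterion 2 only through 2e, separating any enrolled under the printed wording.

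The cost is one line of eligibility text in an amendment. No new test is needed, since marrow immunohistochemistry is already part of the baseline evaluation (Section 4.1.1, item 17), and the optional count uses eligibility records that Section 2.2.3 already requires.
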